5. INVESTIGATIONAL PLAN

5.1. Overall Study Design

This is a seamless Phase 2/3, double-blind, randomized, placebo-controlled clinical study in patients diagnosed with PWS. Following consent (or legal guardian consent and patient assent as appropriate), patients will be screened for eligibility to participate in this study.

The Phase 2 portion of the study is to assess safety and tolerability. Dose safety and tolerability decisions will be made in Phase 2. All patients randomized to placebo and to the selected dose level(s) for Phase 3 evaluation will be included in the Phase 3 efficacy evaluation.

The study will consist of the following six similar periods for Phase 2 and Phase 3 of the study:

1. Screening Period (3 weeks)
 - a. Review of eligibility prior to proceeding to the Tolerability Period
2. Tolerability Period (6 weeks)

- a. Determination of randomization eligibility[†]
3. Dose Escalation Period (3 weeks)
4. Maintenance Period (24 weeks)[‡]
5. Taper Period (2 weeks)[‡]
6. Follow-Up Period (2 weeks)[‡].

[†]Patients who do not meet criteria for randomization eligibility will not be randomized to study SCOUT-015.

[‡]All patients participating in the Maintenance Period may be offered participation in the long-term extension study (SCOUT-016). Patients who do not enroll in the SCOUT-016 study will have their IP tapered over 2 weeks (14 days), followed by a 2-week (14-day) safety follow-up.

After approximately 45 patients complete 4 weeks of the Maintenance Period of the Phase 2 part of the study, the Data Monitoring Committee (DMC) will meet to review safety and tolerability data and to recommend 1 or 2 RAD011 dose level(s) for evaluation in the Phase 3 part of the study. Details regarding the dose selection for the Phase 3 part of the study will be described in the DMC charter.

A schematic overview of the study is presented in [Figure 2](#) for the Phase 2 part, and in [Figure 3](#) for the Phase 3 part.

Screening Period (3 weeks, Visit 1 [Weeks -3 to 0])

Phase 2 and Phase 3 of the study

All patients with a signed informed consent/assent will undergo Screening assessments. Screening assessments will include a full medical history and physical exam, a review of documentation of PWS diagnosis, an ECG, laboratory assessments, and questionnaires (including the HQ-CT) as described in [Section 5.8.2](#). To be eligible for the Tolerability Period, patients must meet the following criterion:

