The dose escalation schema for the DMC-recommended Phase 3 dose level(s) will follow the same dose escalation schedule as in the Phase 2 part of the study. Details of the dose escalation schema are provided in [Table 4](#). Patients' weight at Visit 5 (Last Tolerability Period visit / first Dose Escalation Period visit) will be used to determine the patient's actual doses (mL/day) to be administered from Visit 5 (Week 7) through Visit 14 (Week 34).

The Investigator, or designee, will contact patients/caregivers by phone call, video call, email, or other remote means of communication at Visits 6 (Week 8) and 7 (Week 9) to determine if the patient's dose may be escalated to the next dose level. Dose reductions will not be allowed during the Dose Escalation Period. If a patient cannot be escalated to the next dose level, the patient will be discontinued from the study.

Maintenance Period (24 weeks, Visits 8 to 14 [Weeks 10 to 34])

Phase 2 and Phase 3 of the study

After completing the 3-week Dose Escalation Period, patients will enter the 24-week Maintenance Period. Patients' weight at Visit 5 (last Tolerability Period visit / first Dose Escalation Period visit) will be used to determine the patient's actual doses (mL/day) to be administered between Visits 8 (Week 10) and 14 (Week 34).

Some patients may have their dose adjusted based on tolerability during the Maintenance Period as detailed in [Section 5.7.2](#).

[figure not shown]
After completion of the Maintenance Period, patients may be offered the opportunity to enroll in the long-term extension study (SCOUT-016). Patients who do not elect to enroll will be tapered off the IP.

Taper Period (14 days, Visit 14 [Week 34]) and Follow-up Period (14 days, Visits 15 and 16 [Weeks 36 and 38])

Patients who do not enroll in the long-term extension study (SCOUT-016) will have their IP tapered off over 14 days according to the following schedule: the IP should be decreased by 50% during the first 7 days, followed by an additional 50% during the following 7 days and then discontinued. The taper schedule may be modified at the discretion of the Investigator but cannot

be extended to a total period lasting more than 14 days. A final follow-up will be conducted 2 weeks after the last dose of IP for patients who are tapered off as described in [Section 5.8.6](#).

[figure not shown]
Figure 2: Study Design Schematic – Phase 2 of the Study

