^b The Taper and Follow Up Period visits (Visits 14 to 16) are only for patients who do not proceed to enroll in the active long-term extension study SCOUT-016 and who are tapering off the IP. Patients will return to the site for assessment of concomitant medications, AEs, and to return and reconcile IP on Visit 15. Visit 16 may be done remotely ([Section 5.8.6](#)).

^c To be performed in person at the research site.

^d All assessments must be performed prior to dosing, unless specified otherwise.

^e Assessments may be conducted remotely via a phone call, video call, or other remote means of communication. Dispensing of IP may be done at the research site or remotely, using direct-to-patient shipping methods in accordance with all local laws and regulations. Sites may elect to conduct the entire visit in person.

^f At Week 9 (Visit 7), Week 23 (Visit 11), and Week 30 (Visit 13), patients will be instructed to record the time of their evening and morning doses of study medication on the night prior to and the day of their next clinic visit with the type of meal administered. Patients should also be contacted approximately 1 week prior to their next visit to remind them to complete their food diary prior to their next visit ([Section 10.1.14](#)).

^g At visit 14, patients may be offered participation in the long-term extension study SCOUT-016. Patients eligible and electing to participate in the long-term extension study SCOUT-016 should continue treatment with IP as per the SCOUT-016 protocol. Patients who are not eligible or decide not to participate in the long-term extension study SCOUT-016 should proceed to the Taper and Follow-Up Periods (footnote b, [Section 5.8.5.1](#)).

^h Weight and height must be documented at every in-person visit ([Section 10.1.3](#)).

ⁱ Vital signs include BP, HR, RR, oxygen saturation, and temperature ([Section 10.1.2](#)).

^j A full physical exam should be performed at Week 7 (Visit 5). Other physical exams should be abbreviated, symptom directed ([Section 10.1.4](#)).

^k To be performed at Visit 15 (Week 36) only.

^l If a caregiver is required to assist the patient in completing the questionnaire, the same caregiver should be available throughout the study.

^m When possible, study questionnaires should be completed prior collection of ECG and blood samples.

ⁿ Patients meeting all inclusion and exclusion criteria should proceed to randomization.

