6.3.1. Discontinuation of Investigational Product

The IP may be prematurely discontinued by the patient or the Investigator for reasons including, but not limited to:

- Patient's inability to comply with protocol requirements
- The IP is no longer in the patient's best interest, at the Investigator's discretion
- Patient's decision to discontinue the IP
- Discontinuation due to patient becoming pregnant
- An unexpected, related SAE, or a SUSAR
- Requirement for prohibited concomitant medication ([Section 7.2](#)).

Patients who discontinue IP but do not withdraw consent/assent will continue to be followed according to the planned Schedule of Assessments but will not undergo drug dispensing or drug accountability. Patients who are unwilling or unable to complete planned assessments should undergo the End of Study Visit Assessments (Visit 14, Week 34).

Patients who discontinue IP may have their IP tapered over up to 14 days, at the Investigator's discretion.

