6.3.3. Patient Withdrawal

The Investigator should withdraw the patient from the study if they believe that participation is no longer in the patient's best interest, or in the event of study termination by the Sponsor. If the patient elects to withdraw from the study, reason(s) for withdrawal should be documented. The Investigator will discuss with the patient procedures for withdrawal and any additional care or treatment alternatives available at that time. In addition, patients unable to tolerate the 0.1 mL/kg/day dose level during the Tolerability Period or their assigned dose level(s) during the Dose Escalation Period will be withdrawn from the study.

If a patient withdraws consent/assent from the study, the patient should be encouraged to complete all End of Study Visit assessments (Visit 14, Week 34) completed as described in the Schedule of Assessments ([Table 7](#)). At time of withdrawal of consent/assent, the patient will be withdrawn from all additional study procedures and follow-up.

Data collected until patient withdrawal will be retained and included in the analysis of the study in accordance with local rules and regulations.

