7.1.1. Tapering of Investigational Product for Patients Entering the Taper and Follow-Up Periods

For patients not participating in the long-term extension study (SCOUT-016) and entering the Taper and Follow-Up Periods, the IP will be tapered over 14 days. Following completion of Visit 14 (End of Study/Week 34 Visit), the IP should be decreased by 50% during the first 7 days, followed by an additional 50% taper during the following 7 days and then discontinued. The taper schedule may be modified at the discretion of the Investigator but cannot occur over a longer time than 14 days. A final safety follow-up will be conducted 14 days after the IP is discontinued for patients who do not elect to continue into the long-term extension study.

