10.2. Adverse and Serious Adverse Events

10.2.1. Evaluation of Safety

Timely, accurate, and complete reporting and analysis of safety information from clinical studies are crucial for the protection of patients and is mandated by Regulatory Agencies worldwide. All clinical studies sponsored by Radius will be conducted in accordance with SOPs that have been established to conform to regulatory requirements worldwide to ensure appropriate reporting of safety information.

Where possible, a diagnosis rather than a list of symptoms should be recorded. All AEs should be captured on the appropriate AE pages in the electronic case report form (eCRF) and in source documents.

All AEs will be collected from the time of consent/assent until the following time points:

- For patients who are not enrolled: until time of screen failure
- For enrolled patients:
 - For patients continuing in the long-term extension study SCOUT-016: through Visit 14 (Week 34) inclusively
 - For patients entering the follow-up period with IP tapering: through Visit 16 (Week 38).

Investigators are not obligated to actively seek AEs or SAEs after the participant has concluded study participation. However, if the investigator learns of any SAE, including a death, at any time after a participant has completed the study or 30 days after the last dose of IP, and he/she considers the event to be reasonably related to the study intervention, the investigator must promptly report the SAE.

All patients will be queried using non-leading questions about the occurrences of AEs at each study visit. Adverse events spontaneously reported by the patient and/or in response to an open question from the study personnel or revealed by observation will be recorded during the study at the investigational site. When possible, a constellation of signs and/or symptoms should be identified as one overall event or diagnosis. All AEs for enrolled patients will be recorded in the eCRF and the patient's source documents. Any AEs for patients who are screened but not subsequently enrolled in the study will be recorded only in the patient's source documents. The following data should be documented for each AE by the Investigator:

- Description of the event term as diagnosis, in standard medical terminology when possible
- Classification of "serious" or "not serious"

- Date and time of the onset and resolution (if applicable)
- Severity
- Causal relationship to study drug
- Action taken with study drug

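### Patients withdrawn for intolerance without a taper have no scheduled post-dose collection of new non-serious adverse events

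*Protocol*

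**What the plan says.** **Patients at the end of Maintenance.** Section 5.1 says that those not entering SCOUT-016 "will have their IP tapered over 2 weeks (14 days), followed by a 2-week (14-day) safety follow-up". Its taper and follow-up paragraph adds: "A final follow-up will be conducted 2 weeks after the last dose of IP for patients who are tapered off". Footnote b of Table 7 says that Visits 14 to 16 of the taper and follow-up periods "are only for patients who do not proceed to enroll in the active long-term extension study SCOUT-016 and who are tapering off the IP". Section 7.1.1, headed for patients entering those periods, words the population differently: "A final safety follow-up will be conducted 14 days after the IP is discontinued for patients who do not elect to continue" into the extension.

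**Patients who stop early.** Section 6.3.1 says: "Patients who discontinue IP may have their IP tapered over up to 14 days, at the Investigator's discretion". It also keeps patients who stop investigational product (IP) without withdrawing consent on the planned schedule. Patients unwilling or unable to do that should have the Visit 14 assessments.

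**Patients who cannot tolerate the dose.** Section 6.3.3 says that patients unable to tolerate "their assigned dose level(s) during the Dose Escalation Period will be withdrawn from the study", and Section 5.7.1 agrees. Section 5.1 discontinues from the study anyone who cannot be escalated. Section 5.7.2 does the same, in consultation with the sponsor, for anyone needing a second reduction in Maintenance.

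**End of AE collection.** For enrolled patients, Section 10.2.1 has two entries. One is for SCOUT-016 entrants, through Visit 14. The other reads: "For patients entering the follow-up period with IP tapering: through Visit 16 (Week 38"). Section 10.2.2 repeats the same two groups. Section 10.2.1 adds that investigators need not actively look for events once participation has ended.

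**The concern.** Post-treatment follow-up depends on tapering, and tapering is optional for the patients most likely to leave because of the drug. Someone who stops abruptly for intolerance and is taken out of the study has no listed end date for AE collection. No contact is scheduled after the last dose beyond early-termination assessments, whose timing relative to that dose is not set.

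Two things are at stake. First, Section 11.4.5 summarizes treatment-emergent AEs by treatment group. If patients in one arm leave this way more often, that arm is observed for less time after dosing, and its count of new non-serious events is lower for that reason alone. An analysis-plan definition of treatment emergence cannot recover events that were never collected. Second, Section 6.3.2 itself warns that liver injury can appear or worsen after the drug is stopped, and Section 10.2.1.5 makes hepatic dysfunction and suicidality events of special interest. A first non-serious event of either kind after withdrawal has no scheduled point of capture.

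**Working it through.** The protocol states no figure for this point, so the check is to trace each route off treatment through the rules.

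| Route | Post-dose follow-up | End of AE collection |
|---|---|---|
| Completes Maintenance, enters SCOUT-016 | Under that study | Visit 14 (10.2.1, 10.2.2) |
| Completes Maintenance, does not enter, tapers | 14 days after last dose (5.1, 7.1.1) | Visit 16 (10.2.1, 10.2.2) |
| Stops IP, stays in the study | Planned schedule with AE review (6.3.1) | Not listed, but the visits continue |
| Removed for intolerance, tapers by discretion | Falls within the wording of 5.1 and footnote b | Visit 16 by the wording of 10.2.1 |
| Removed for intolerance, no taper | None scheduled beyond early-termination assessments | Not listed |

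The last row is the gap. Each step to it rests on protocol text: removal from the study (5.1, 5.7.1, 5.7.2, 6.3.3), discretionary taper (6.3.1), follow-up for tapering patients only (5.1, Table 7 footnote b), and two AE end dates, neither of which fits (10.2.1, 10.2.2).

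**What still covers a patient in the last row**
- Serious AEs and deaths up to 30 days after the last dose, whatever the causality (10.2.2).
- AEs already recorded, followed to resolution or stabilization, or until before database lock (10.2.2, 10.2.3). Possible liver injury is followed to normal or baseline (6.3.2).
- Pregnancies within 30 days of the last dose (10.2.9).
- Encouragement to return for a safety assessment, with no visit or time given (10.2.2).
- Early-termination assessments at Visit 14, labelled as such in Table 7 and including AE review, with no interval from the last dose.

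None of these is a scheduled collection of new non-serious events after stopping.

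**Scale**
- Section 11.1 counts 15 Phase 2 patients randomized to one unselected dose, and 30 for two: 30 / 2 = 15 per dose.
- The number removed for intolerance without a taper is not given. Assume 1 to 3 per dose: 1 / 15 = 7% and 3 / 15 = 20%.
- For the primary analysis groups, the assumed 15% dropout gives 0.15 × 176 = 26.4 patients with two doses, or 0.15 × 118 = 17.7 with one. These are leavers for any reason, so under the plan's own assumption they bound the affected group from above.

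**The case against.** The strongest reply is that the passages describe different populations and do not conflict. Sections 5.1 and 7.1.1 deal with patients who finish Maintenance and do not enter SCOUT-016. All of them are to be tapered, so being tapered off and not continuing pick out the same people. Section 6.3.1 then deals with early stoppers. Much of this stands: the fault is mainly a case that no rule covers. But Sections 10.2.1 and 10.2.2 set the AE end date for enrolled patients in general, and this group is missing from both.

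It can also be said that many early stoppers are followed for longer than 14 days, because Section 6.3.1 keeps them on schedule. That is true, and it confines the point to patients removed from the study.

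Four stronger readings are tempting, and the documents do not support them:
- **That no AEs at all are collected after the last dose.** The 30-day rule for serious events, the follow-up of recorded AEs and the pregnancy rule contradict this. Nor is zero days of follow-up a stated figure, because the early-termination assessments have no fixed interval from the last dose.
- **That the course of events after stopping is lost for causality judgement.** The AE that prompted withdrawal is already recorded and is followed under Sections 10.2.2 and 10.2.3.
- **That 1 to 3 withdrawals would be 10% to 30% of a Phase 2 dose group**, from 45 × 2/9 = 10. The 45 are patients completing 4 weeks of Maintenance, which excludes anyone withdrawn during Dose Escalation. The figure of 15 randomized per dose is the appropriate one.
- **That Visit 16 is wrongly fixed at Day 260.** Sections 5.1 and 7.1.1 time the follow-up from the last dose, and Day 260 is the nominal day for a taper ending at Day 246 (246 + 14 = 260).

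**Conclusion.** The point holds in a limited form. For patients removed from the study for intolerance who stop without a taper, the protocol sets neither a scheduled post-dose contact nor an AE-collection end date. New non-serious AEs after stopping are therefore not systematically collected, and the comparison of treatment-emergent AEs by arm rests on unequal windows.

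The size cannot be derived from the protocol. The 7% to 20% of a Phase 2 dose group rests on an assumed 1 to 3 such patients. A difference between arms also requires that such withdrawals differ by arm. It is plausible that they rise with dose, but the protocol gives no figure for this. The effect on Phase 2 dose selection is probably limited, because the withdrawal and its triggering AE are recorded and available to the Data Monitoring Committee. The main loss is in safety characterization. The change is worth making because it is cheap.

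**What to change.** Reconcile Section 5.1 (taper and follow-up), Table 7 footnote b, and Sections 6.3.1, 7.1.1, 10.2.1 and 10.2.2. Every randomized patient who stops IP, leaves the study and does not enter SCOUT-016 should have the same AE-collection end point timed from the last dose, tapered or not. One way is to extend the protocol's existing 14-day remote follow-up contact to them and add a third entry for this group to the end-date lists in Sections 10.2.1 and 10.2.2.

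This is a data-collection rule only. Who tapers and who is withdrawn is for the sponsor to reconcile. The cost is protocol wording and one remote contact per early leaver.

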5.2. Scientific Rationale for Study Design

Despite a large safety database with a well-characterized safety profile and dose-response relationship of EPIDIOLEX in multiple indications, data on safety and efficacy of CBD remains limited in patients with PWS. However, as PWS is a rare disease with significant unmet needs, multiple large-scale studies would be impractical and may delay access to efficacious therapies.

Therefore, this study is designed as a seamless Phase 2/3 study to assess safety and tolerability of multiple candidate doses in Phase 2 of the study (10 to 40 mg/kg/day), followed by Phase 3 of the study. In Phase 3 of the study, 1 or 2 candidate dose level(s) will be recommended by the DMC for further development and assessment based on safety and tolerability data. This approach will allow a streamlined way to confirm the safety and tolerability profile of RAD011 in patients with PWS while limiting the number of patients exposed to lesser tolerated doses. In addition, data from patients who participated in Phase 2 of the study in the dose group(s) chosen for continued development and assessment in Phase 3 of the study will contribute to the overall intent-to-treat (ITT) population. This, in turn, allows for more efficient recruitment in this rare disease population.

The double-blind design will minimize patient and Investigator bias, whereas the placebo control will allow better delineation of efficacy and safety profiles of RAD011. The use of placebo groups in this study is acceptable as there are no FDA approved treatments for hyperphagia in patients with PWS. In addition, the IP will be administered in addition to standard of care therapy, which can include GH supplementation and any additional behavioral interventions that have been implemented and maintained stable throughout the study.

The 3-week Screening Period and the 6-week Tolerability Period will allow for the characterization of HQ-CT scores and help minimize potential bias in patient/caregiver completion of the HQ-CT questionnaire. These Periods will result in the exclusion of patients with too low mean scores or significant changes from Screening to the end of the Tolerability Period without any active treatment. The 6-week duration of the Tolerability Period will be sufficient to evaluate the HQ-CT scores and the tolerability of the MCT vehicle used in the RAD011 formulation. The use of inactive treatment periods in PWS studies is common as there is a recognized variability in hyperphagia behavior and HQ-CT response behaviors.

Once randomized, patients will enter the 3-week Dose Escalation Period followed by a 24-week Maintenance Period. This combined 26-week treatment period was designed to allow for potential placebo effect to wane and allow for the evaluation of separation of effects between placebo and RAD011 groups.

The target population for this study has also been carefully selected to include patients with moderate to severe hyperphagia (HQ-CT scores ≥ 13) ([Fehnel, 2015](#)). This is in line with baseline severity in other PWS development programs. In terms of age, the primary efficacy analysis will be based on the modified ITT (mITT) population ([Section 11.4.1](#)) which comprises patients aged 12 to 65 years. However, as the median age of transition into Phase 3 hyperphagia is 8 years (interquartile range of 5 to 13 years), patients aged 8 to < 12 years may also benefit from efficacious hyperphagia management ([Miller, 2011](#)). However, since a significant proportion of patients below the age of 12 years may not have established hyperphagia because developmental milestones may significantly affect food-seeking behaviors and environmental interactions, and

because families are in the process of instating environmental controls, hyperphagia may not be well established or stable prior to 12 years of age. Inconsistent, less severe, or unestablished hyperphagia may therefore render efficacy assessment impossible. In addition, the population aged <12 years with severe hyperphagia remains limited, thereby enhancing the difficulty of recruiting such patients. For these reasons, and given the small sample size of Phase 2 of the study, patients aged 8 to <12 years of age will not be included in Phase 2 of the study, but will be allowed to randomize in Phase 3 of the study in order to obtain safety and preliminary efficacy data.

